9.2 Comparable Methods

Proposed methods represent standard technology for drug and hormone concentration measurement in plasma and tissue; for IHC, and for blood coagulation protein profiling as well as IGF-1/IGFBP-3 and SHBG proteins in plasma samples. Gene expression will be examined using Nanostring, which is a relatively new but now fairly standard method for measuring gene expression in paraffin embedded samples.

10.1.2 Research Assay Laboratories are as follows

The Pathology Core Facility (PCF) at the Robert H. Lurie Comprehensive Cancer Center of Northwestern University will receive serum, plasma and breast tissue samples from all participating study sites (except for serum pregnancy tests, which will be processed by the clinical laboratories at each accrual site). The distribution of samples to appropriate central labs for assays as listed below will be performed by the Pathology Core Facility, as directed by [name] laboratory personnel. Details of shipping are provided in section 10.3.

Drug concentration assays of tissue and plasma samples and plasma steroid hormone assays will be performed by the laboratory of [name] at the Illinois Institute of Research (IITRI), using LC/MS/MS protocols established for our prior studies[16, 17][45].

Cell proliferation and progesterone receptor IHC at baseline and after treatment will be performed in the Pathology Core Facility of the Robert H. Lurie Comprehensive Cancer Center.

Plasma hormone levels for steroid hormones: estradiol, progesterone, dehydroepiandrosterone (DHEA), androstenedione and testosterone to be measured by LC/MS/MS in the laboratory of [name] at the Illinois Institute of Research (IITRI).

Plasma concentrations of IGF-1/IGFBP-3 and SHBG: IGF-1 and its binding proteins IGFBP-3, and SHBG [16, 46] to be measured by ELISA assays at Northwestern University, Comprehensive Metabolic Core.

Plasma levels of coagulation cascade proteins: four blood coagulation protein assays [Factor VIII, factor IX, von Willebrand factor (vWF), and Protein S] using plasma samples to be performed at Hemostasis Laboratory, Northwestern Memorial Hospital.

10.2 Collection and Handling Procedures

All participating sites will receive specific instructions for collection, processing and shipment of samples and specimen to the PCF at NU.

Refer to Specimen Manual.

10.3 Shipping Instructions

All samples will be shipped in compliance with the International Air Transport Association (IATA) Dangerous Goods Regulations.

Refer to Specimen Manual.

10.4 Tissue Banking

Biologic specimens collected during the conduct of each clinical trial that are not used during the course of the study will be considered deliverables under the contract and thus the property of the NCI. At study completion, NCI reserves the option to either retain or relinquish ownership of the unused biologic specimens. If NCI retains ownership of specimens, the Contractor shall collect, verify and transfer the requested biologic specimens from the site to a NCI-specified repository or laboratory at NCI's expense.

11. REPORTING ADVERSE EVENTS

DEFINITION: AE means any untoward medical occurrence associated with the use of a drug in humans, whether or not considered drug related. An AE can therefore be any unfavorable and unintended sign), symptom, or disease temporally associated with participation in a study, whether or not related to that participation. This includes all deaths that occur while a participant is on a study.

Please note that all abnormal clinical laboratory values that are determined to be of clinical significance based on a physician's assessment are to be reported as AEs. Those labs determined to be of no clinical significance or of unknown clinical significance (per the physician's assessment) should not be reported as AEs. Any lab value of unknown clinical significance should continue to be investigated/followed-up further for a final determination, if possible.

A list of AEs that have occurred or might occur can be found in §6.2 Reported Adverse Events and Potential Risks, as well as the Investigator Brochure or package insert.

11.1 Adverse Events

11.1.1 Reportable AEs

All AEs that occur after the informed consent is signed and baseline assessments are completed must be recorded on the AE CRF (paper and/or electronic) whether or not related to study agent.

Table 1. A modified CTCAE for assessing skin application AEs.

Table 1 Modified CTCAE for assessing skin toxicity of endoxifen gel applied to the breast skin. These	
assessments will be made on the breast skin (application site).	

	assessments will be made on t	ne breast skill (application	5,10,1
	Grade 1	Grade 2	Grade 3
Dry Skin	No erythema or pruritus	With erythema or pruritus	With erythema and pruritus
Pain of Skin	Mild pain	Moderate pain	Severe pain
Photosensitivity	Painless erythema	Mild to moderate pain with erythema	Erythema with blistering
Pruritus	Mild, requiring topical intervention	Intense, with changes from scratching, oral intervention needed	Intense, constant, limiting ADL or sleep, oral steroids needed.
Rash maculopapular	Macules or papules <25% of treated area, with or without symptoms (pruritus, burning, tightness)	Macules or papules >25% of treated area, with or without symptoms (pruritus, burning, tightness), limiting instrumental ADL	Macules or papules > 25% of treated area, with or without symptoms (pruritus, burning, tightness), limiting self-care ADL
Urticaria	Asymptomatic or mild symptoms, not requiring therapy	Moderate; limited local therapy needed, limiting instrumental ADL	Urticarial lesions covering >30% of application area; oral or IV intervention needed

11.1.2 AE Data Elements:

The following data elements are required for AE reporting.

- AE verbatim term (AEs which occur on the breast should include "application site" in the verbatim term).
- NCI Common Terminology Criteria for Adverse Events version 4.0 (CTCAE v4.0) AE term (MedDRA lowest level term)
- CTCAE (MedDRA) System Organ Class (SOC)
- · Event onset date and event ended date
- Treatment assignment code (TAC) at time of AE onset
- Severity grade
- Attribution to study agent (relatedness)
- Whether or not the event was reported as a SAE
- Whether or not the subject dropped due to the event
- Outcome of the event

11.1.3 Severity of AEs

11.1.3.1 Identify the AE using the CTCAE version 4.0. The CTCAE provides descriptive terminology (MedDRA lowest level term) and a grading scale for each AE listed. A copy of the CTCAE can be found at http://ctep.cancer.gov/protocolDevelopment/electronic applications/ctc.htm

AEs will be assessed according to the grade associated with the CTCAE term. AEs that do not have a corresponding CTCAE term will be assessed according to the general guidelines for grading used in the CTCAE v4.0. as stated below.

CTCAE v4.0 general severity guidelines:

Grade	Severity	Description
1	Mild	Mild; asymptomatic or mild symptoms; clinical or diagnostic observations only; intervention not indicated.
2	Moderate	Moderate; minimal, local or noninvasive intervention indicated; limiting age-appropriate instrumental activities of daily living (ADL)*.
3	Severe	Severe or medically significant but not immediately life-threatening; hospitalization or prolongation of hospitalization indicated; disabling; limiting self-care ADL**.
4	Life-threatening	Life-threatening consequences; urgent intervention indicated.
5	Fatal	Death related to AE.

ADL

- *Instrumental ADL refers to preparing meals, shopping for groceries or clothes, using the telephone, managing money, *etc*.
- **Self-care ADL refers to bathing, dressing and undressing, feeding self, using the toilet, taking medications, and not bedridden.

11.1.4 Assessment of relationship of AE to treatment

The possibility that the AE is related to study agent will be classified as one of the following: not related, unlikely, possible, probable, and definite.

11.1.5 Follow-up of AEs

All AEs, including lab abnormalities that in the opinion of the investigator are clinically significant, will be followed according to good medical practices and documented as such.

11.2 Serious Adverse Events

- 11.2.1 DEFINITION: Regulations at 21 CFR §312.32 (revised April 1, 2014) defines an SAE as any untoward medical occurrence that at any dose has one or more of the following outcomes:
 - Death
 - A life-threatening AE
 - Inpatient hospitalization or prolongation of existing hospitalization
 - A persistent or significant incapacity or substantial disruption of the ability to perform normal life functions
 - A congenital anomaly or birth defect
 - Important medical events that may not be immediately life-threatening or result in death or hospitalization should also be considered serious when, based upon appropriate medical judgment, they may jeopardize the patient and may require intervention to prevent one of the other outcomes.

The planned mastectomy procedure will not be considered to be an SAE.

11.2.2 Reporting SAEs to DCP

11.2.2.1 The Lead Organization and all Participating Organizations will report SAEs on the DCP SAE Report Form found at http://prevention.cancer.gov/clinical-trials/clinical-trials-management/protocol-information-office/pio-instructions-and-tools/2012-consortia.

11.2.2.2 Contact the DCP Medical Monitor by phone within 24 hours of knowledge of the event.

Name: [name]

Address: Division of Cancer Prevention

National Cancer Institute

[name]

[name]

[contact] (during normal business hours)

[contact]

Email: [contact]

Include the following information when calling the Medical Monitor:

- Date and time of the SAE
- Date and time of the SAE report
- Name of reporter
- Call back phone number
- Affiliation/Institution conducting the study
- DCP protocol number
- Title of protocol
- Description of the SAE, including attribution to drug
- 11.2.2.3 The Lead Organization and all Participating Organizations will email written SAE reports to the following people within 48 hours of learning of the event using the fillable PDF SAE Report Form:
 - The NCI/DCP Medical Monitor
 - DCP's Regulatory Contractor CCS Associates, Inc. (CCSA; [contact]) at [contact]
 - Northwestern Cancer Prevention Consortium (NCPC, [contact]) at [contact]
- 11.2.2.4 The DCP Medical Monitor and CCSA regulatory and safety staff will determine which SAEs require FDA submission as IND safety reports.
- 11.2.2.5 The Lead Organization and all Participating Organizations will comply with applicable regulatory requirements related to reporting SAEs to the IRB/IEC.

11.2.3 Follow-up of SAE

Site staff should send follow-up reports as requested when additional information is available. Additional information should be entered on the DCP SAE Report Form in the appropriate format. Follow-up information should be sent to DCP, CCSA, and NCPC as soon as available. Subjects who experience an SAE will be followed for 30 days or until resolution.

12. STUDY MONITORING

12.1 Data Management

Data will be managed by the study statistician, [name], according to standard operating procedures, which meet the guidelines of DCP Requirements for Data Management and which follow the Data Management Plan that Northwestern University has on file with the Division of Cancer Prevention, NCI. Source data verification will be performed by the Department of Clinical Research Services. The Consortia 2012 Data Management Plan, submitted as part of a contract agreement with the NCI (HHSN261201200035I), was approved.

12.2 Case Report Forms

Participant data will be collected using protocol-specific case report forms (CRFs) developed from the standard set of DCP Chemoprevention CRF Templates and utilizing NCI-approved Common Data Elements (CDEs). The approved CRFs will be used by Northwestern University to create the electronic CRFs (e-CRFs) screens in the Robert H. Lurie Comprehensive Cancer Center Clinical Trials Management System (CTMS). Site staff will enter data into the e-CRFs for transmission to DCP according to DCP standards and procedures.

12.3 Source Documents

All source documents will be collected and stored in the Clinical Research Office of the site where the participant was accrued. Any data recorded directly on CRFs that constitute no prior written or electronic record of data, will be specifically identified as source data. BESS questionnaire completed in person may be completed directly on the electronic CRF and need not be transcribed from separate source documentation.

12.4 Data and Safety Monitoring Plan

A comprehensive Data Safety and Monitoring Plan has been submitted by Northwestern University, approved by the DCP, and is on file there. Any future changes will be forwarded for review.

12.5 Sponsor or FDA Monitoring

The NCI, DCP (or their designee), pharmaceutical collaborator (or their designee), or FDA may monitor/audit various aspects of the study. These monitors will be given access to facilities, databases, supplies and records to review and verify data pertinent to the study.

12.6 Record Retention

Clinical records for all participants, including CRFs, all source documentation (containing evidence to study eligibility, history and physical findings, laboratory data, results of consultations, *etc.*), as well as IRB records and other regulatory documentation will be retained by the Investigator in a secure storage facility in compliance with Health Insurance Portability and Accountability Act (HIPAA), Office of Human Research Protections (OHRP), Food and Drug Administration (FDA) regulations and guidances, and NCI/DCP requirements, unless the standard at the site is more stringent. The records for all studies performed under an IND will be maintained, at a minimum, for two years after the approval of a New Drug Application (NDA). For NCI/DCP, records will be retained for at least three years after the completion of the research. NCI will be notified prior to the planned destruction of any materials. The records should be accessible for inspection and copying by authorized persons of the Food and Drug Administration. If the study is done outside of the United States, applicable regulatory requirements for the specific country participating in the study also apply.

12.7 Clinical Supply Agreement

The agents, ENX gel and placebo gel, are supplied by DCP, NCI, where they were developed by investigators in the PREVENT Program. Therefore, the following obligations/guidelines, in addition to the provisions in the "Intellectual Property Option to Collaborator contained within the terms of award, apply to the use of Agent(s) in this study:

- 12.7.1 Agent(s) may not be used for any purpose outside the scope of this protocol, nor can Agent(s) be transferred or licensed to any party not participating in the clinical study. Collaborator(s) data for Agent(s) are confidential and proprietary to Collaborator(s) and shall be maintained as such by the investigators. The protocol documents for studies utilizing investigational agents contain confidential information and should not be shared or distributed without the permission of the NCI. If a patient participating on the study or participant's family member requests a copy of this protocol, the individual should sign a confidentiality agreement. A suitable model agreement can be downloaded from the DCP website.
- 12.7.2 For a clinical protocol where there is an Investigational Agent used in combination with (an) other investigational Agent(s), each the subject of different collaborative agreements, the access to and use of data by each Collaborator shall be as follows (data pertaining to such combination use shall hereinafter be referred to as "Multi-party Data").
- 12.7.3 NCI must provide all Collaborators with prior written notice regarding the existence and nature of any agreements governing their collaboration with NIH, the design of the proposed protocol, and the existence of any obligations that would tend to restrict NCI's participation in the proposed combination protocol.
- 12.7.4 Each Collaborator shall agree to permit use of the Multi-Party Data from the clinical trial by any other Collaborator solely to the extent necessary to allow said other Collaborator to develop, obtain regulatory approval, or commercialize its own investigational agent.
- 12.7.5 Any Collaborator having the right to use the Multi-Party Data from these trials must agree in writing prior to the commencement of the trials that it will use the Multi-Party Data solely for development, regulatory approval, and commercialization of its own investigational agent.
- 12.7.6 Clinical Trial Data and Results and Raw Data developed under a collaborative agreement will be made available exclusively to Collaborator(s), the NCI, and the FDA, as appropriate. All data made available will comply with HIPAA regulations.
- 12.7.7 When a Collaborator wishes to initiate a data request, the request should first be sent to the NCI, who will then notify the appropriate investigators of Collaborator's wish to contact them.
- 12.7.8 Any manuscripts reporting the results of this clinical trial must be provided to DCP for immediate delivery to Collaborator(s) for advisory review and comment prior to submission for publication. Collaborator(s) will have 30 days (or as specified in the CSA) from the date of receipt for review. Collaborator shall have the right to request that publication be delayed for up to an additional 30 days in order to ensure that Collaborator's confidential and proprietary data, in addition to Collaborator(s)'s intellectual property rights, are protected. Copies of abstracts must be provided to DCP for forwarding to Collaborator(s) for courtesy review as soon as possible and preferably at least three days prior to submission, but in any case, prior to presentation at the meeting or publication in the proceedings. Press releases and other media presentations must also be forwarded to DCP prior to release. Copies of any

manuscript, abstract, and/or press release/ media presentation should be sent to the Protocol Information Office at NCI DCP [contact].

The Protocol Information Office will forward manuscripts to the DCP Project Officer for distribution to the Collaborator(s). No publication, manuscript or other form of public disclosure shall contain any of Collaborator's confidential/proprietary information.

13. STATISTICAL CONSIDERATIONS

13.1 Study Design/Description

We plan a randomized, double-blind, Phase I trial with a control arm and a treatment arm, with dose escalation from 10 mg ENX gel daily (5 mg per breast) to 20 mg daily (10 mg per breast). Dose-limiting toxicity is defined as the occurrence of Grade 2 or greater skin response for any of the CTCAE parameters listed in Table 1.

Cohorts 1 and 2 will be randomized 2:1 (ENX gel and placebo). Cohort 3 will consist only of actively treated subjects. We planned that the sample size may range up to 38, depending on the frequency of DLT, and how early in each cohort DLT was observed. After completion of Cohort 2 (with accrual of 12 subjects each in Cohort 1 and 2), we will now accrue 8 subjects in Cohort 3, with a final accrual of 32 subjects. All subjects who receive any study drug will be evaluable for the primary endpoint of dermal toxicity.

[figure not shown]
We choose a 2:1 randomized design with a placebo arm with each dose in *order to establish variability of measurements when no treatment is applied*, and yet to provide treatment to as many subjects as possible. Randomization is double blinded, and the gel used in the treatment and control groups has similar appearance, consistency, and chemical composition, except for the presence of ENX in the active gel. The study will employ intent to treat principles. Although formal statistical comparison will be limited by the small sample size (as can be the case for Phase I trials), the placebo group will be used to interpret subjective symptoms such as skin irritation or pruritis. Combining placebo groups will yield a total of n=8, thus providing standard error of the estimate of SD/sqrt(8) and 0.5/sqrt/(8).

13.2 Randomization/Stratification

Randomization list will be provided by study statistician and made available to the accrual-site pharmacists. Neither stratification nor blocking will be used for demographic factors. Interim analysis for toxicity is built into the design of this escalation study (see the schema). Efficacy determination will be done for each of two doses and placebo groups with purpose of gaining all the information available.

13.3 Accrual and Feasibility

Assuming 38 women for all cohorts, we anticipate recruiting 14 at NU, and 12 each at MSKCC and CS-LA. Women of all races and ethnicities will be recruited. The duration of accrual is expected to be 12-14 months at a rate of 3 subjects per month (one subject per site per month). The anticipated timeline is shown below.

13.4 Primary Objective, Endpoint(s), Analysis Plan

Data Analyses Plans The primary plan is to estimate and provide confidence intervals (CIs) for the incidence of skin irritation in patients treated at each dose level, as well as in the placebo, using CTCAE criteria listed in Table 1. It is expected a wealth of information on parameters of interest will be acquired from placebo group, short of formal testing.

13.5 Secondary Objectives, Endpoints, Analysis Plans

Secondary objectives:

- 1) Comparison of breast tissue concentrations of ENX at each dose will be done using visualization, graphics and by providing appropriate confidence interval (CI).
- 2) Plasma concentrations of ENX at each dose (10 mg per day and 20 mg per day), will be reported as observed concentrations with appropriate CIs.
- 3-5) Relate to comparison of the plasma levels for steroid hormones, plasma estrogenic response proteins, and plasma coagulation parameters. To assess treatment-related changes, the 95%CI of the mean difference post-pre and a test of the central parameter = 0 will be provided as in the previous objective.
- 6) To assess tissue biologic response to ENX gel treatment. These will be compared as pre- and post-therapy values, to explore the potential therapeutic effects of the two doses of ENX: a) by IHC for Ki67, ER, and PR expression; b) by nanostring assays, using a panel of genes reported to change with ENX exposure. For both IHC and gene expression, values for "pre" and for "post" measurements will be subtracted from each other and CIs for the mean difference will be provided. A nonparametric test of the central parameter being zero will be performed.
- 7) To bank germline DNA for future pooled analyses of polymorphisms in tamoxifen metabolizing enzymes, statistical analysis will be used as needed (optional).
- 8) Analysis of symptoms as reported in the BESS questionnaire: This uses scores where the lowest describes "no symptom" and the highest reflects "extremely" or "always". The high scores are adverse. When subtracting post-pre measures, negative values suggest improvement over time, while positive suggest worsening. We will provide graphical displays of these differences as histograms with x-axis values -5, -4, ...0, ... 4, 5 and empirical mass function on the top. To compare the dose groups (low, high) and singular dose versus placebo, if appropriate, we will use the nonparametric two sample Wilcoxon-Mann-Whitney test, with corrections for ties. The study was not specifically powered for such analysis, and resulting one and two sided p-values will be considered descriptive statistics useful for future analyses. Average, median and range of scores for each noted group will be provided as descriptive measures of location and variance. We will use multiple imputation via non-parametric probability integral transformation[53] to impute missing data as appropriate.

All tests will be two-sided. We will use multiple imputation via non-parametric probability integral transformation (Helenowski, PhD Dissertation, 2011) to impute missing data as appropriate.

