1.2 Secondary Objectives

- 1.2.1 To measure the breast tissue concentrations of (E) and (Z) isomers of N- desmethyl-4-hydroxytamoxifen (ENX) and 4-hydroxytamoxifen (4-OHT) at each dose (10 mg per day and 20 mg per day).
- 1.2.2 To measure the plasma concentrations of (E) and (Z) isomers ENX and 4-OHT at each dose (10 mg per day and 20 mg per day).
- 1.2.3 To measure plasma hormone levels for steroid hormones (estradiol, progesterone, dehydroepiandrostenedione [DHEA], androstenedione, testosterone) in comparison to vehicle placebo gel.
- 1.2.4 To measure serum estrogenic response to topical ENX gel therapy in comparison to vehicle placebo gel (sex hormone binding globulin and IGF pathway proteins).
- 1.2.5 To assess changes in coagulation parameters (Factor VIII, Factor IX, vWF, Protein S) in response to ENX gel therapy in comparison to vehicle placebo gel.
- 1.2.6 Using pre- and post-therapy tissue samples, to explore the potential therapeutic effects of the two doses of ENX gel in comparison to vehicle placebo gel: a) by IHC, Ki67 labelling (for cell proliferation), estrogen receptor (ER), progesterone receptor (PR) expression (for estrogen blockade); b) by expression of a panel of genes reported to change with ENX exposure (using nanostring assays).
- 1.2.7 Bank germline DNA for future pooled analyses of polymorphisms in tamoxifen metabolizing enzymes in comparison to vehicle placebo gel (optional).
- 1.2.8 To assess symptoms related to use of endoxifen gel in comparison to vehicle placebo gel, as assessed by the Breast Cancer Prevention Trial (BCPT) Eight Symptom Scale (BESS) questionnaire.

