7.4 Evaluation at Completion of Study Intervention

Study Visits 1 and 2 may be combined on the same day if feasible and convenient (i.e. surgery start time allows completion of Study Visit 1 tasks prior to surgery start time. If this is not possible, Study Visit 1 will occur on the day prior to surgery. Participants will fast from midnight on the evening prior to surgery.

- **7.4.1** Study Visit 1 (Day before surgery, can occur on the day of surgery if feasible for participant to arrive early)
 - 1. BESS questionnaire (Appendix D)
 - 2. Tobacco and Alcohol Use Questionnaires
 - 3. Skin symptoms per CTCAE criteria (Table 1).
 - 4. Breast skin photos, taken only in participants experiencing skin toxicity, and will focus on the area showing the skin toxicity.
 - 5. Collection of last menstrual period date for premenopausal participants
 - 6. Concomitant medications and adverse events assessment
 - 7. Compliance assessment (weighing gel dispensers) and collection of study agent
 - 8. Collection of study diary.

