7.4.2 Study Visit 2 (Day of surgery, day 22-29)

On arrival the following procedures/evaluations will be performed:

- 1. Urine or serum pregnancy test (for subjects of child bearing potential) per standard of care prior to the surgery.
- 2. Medical history per treating physician
- 3. Physical exam. The source document for this may be anesthesia or surgery H&P, completed within 28 days prior to surgery.
- 4. Vital signs assessment per anesthesia assessment or pre-operative nursing evaluation
- 5. Clinical labs for renal and hepatic function including total bilirubin, AST, ALT, alkaline phosphatase, blood urea nitrogen and creatinine
- 6. Blood collection for research purposes:
 - a. Two 3 mL Blue Top tube (citrate) for coagulation panel.
 - b. Two 10mL Lavender top tubes (K₂EDTA) to obtain plasma for hormone level measurement (estradiol, progesterone, and androgens [DHEA (dehydroepiandrosterone), androstenedione, and testosterone]) and measurement of IGF-1, IGFBP-3, and SHBG. Buffy coat will be saved for DNA/RNA isolation for future pooled analyses if the subject consents to this optional study.
- 7. Blood collection should occur prior to completion of the mastectomy (i.e. if blood is not drawn prior to the patient entering the operating room, it can be drawn in the OR).
- 8. Tissue will be obtained from the DCNB as well as the surgical resection specimen for study end points.

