6. ENX-response endpoints in breast tissue samples: Ki67 labeling index, PR and ER expression, and expression of a panel of genes reported to change with ENX exposure, will be measured in breast tissue samples obtained at diagnostic core needle biopsy (CNB) performed prior to study entry, and compared to the measurements in post-therapy surgical

samples. Both Ki67 reduction and increase in PR expression are associated with tamoxifen response [47]. In addition, we will measure expression of genes selected from those modulated by 4-OHT [48] and those affected by ENX [26] in MCF7 breast cancer cells. Hawse et al., have reported that ENX treatment opposed the expression of 28 genes modulated by estradiol alone in MCF7 cell culture [26]. Of these, 12 genes were regulated by both 4-OHT and ENX but not by fulvestrant, and 6 genes were uniquely modulated by ENX but not by 4-OHT or fulvestrant. On the other hand, they also reported that ENX modulates 177 genes that are independent from its effect in opposing estrogen signaling, suggesting that the molecular mechanism of ENX actions differ from those of 4-OHT and fulvestrant [26]. Our recently opened 4-OHT gel study will provide an opportunity to compare gene expression profiles in response to ENX and 4-OHT in tumor samples. At the end of the intervention period, the mastectomy specimen will be sampled to obtain tissue for these measurements. We will use NanoString nCounter® assays (NanoString Inc., Seattle, CA) as a research platform to evaluate differential expression of 100 genes. We will include the 50 genes of the Prosigna Breast Cancer Prognostic Gene Signature Assay (formerly called the PAM50 test): 1) to define tumor subtypes (luminal A/B, Basal, etc.) of core biopsy

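### Objectives 1.2.3 to 1.2.6 are comparisons with placebo gel, but section 13.5 items 3 to 6 test only within-woman change against zero

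*Combined protocol and SAP*

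**What the plan says.** Section 1.2 defines four secondary objectives against placebo. Objective 1.2.3 covers steroid hormones ("androstenedione, testosterone) in comparison to vehicle placebo gel"). Objective 1.2.5 covers changes in coagulation parameters "in response to ENX gel therapy in comparison to vehicle placebo gel". Objectives 1.2.4 (SHBG and IGF proteins) and 1.2.6 (Ki67, ER, PR and gene panel) carry the same comparator.

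Section 13.5 gives the analysis:

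- **Items 3 to 5 (plasma endpoints):** "To assess treatment-related changes, the 95%CI of the mean difference post-pre and a test of the central parameter = 0 will be provided". The sentence goes on to refer to the previous objective, but item 2 describes no test.
- **Item 6 (tissue):** a CI for the mean pre/post difference, then "A nonparametric test of the central parameter being zero will be performed".
- **Item 8 (BESS):** a two-sample Wilcoxon-Mann-Whitney test, including a single dose against placebo if appropriate.

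Section 13.2 plans efficacy determination for each dose and for placebo, so placebo changes may well be reported. Section 13.1 adds: "Combining placebo groups will yield a total of n=8".

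On sampling, section 7.4 says "Participants will fast from midnight on the evening prior to surgery", and section 7.4.2 says of the post-treatment blood that "if blood is not drawn prior to the patient entering the operating room, it can be drawn in the OR". Section 8.2 item 6 takes the tissue markers from samples "obtained at diagnostic core needle biopsy (CNB) performed prior to study entry, and compared to the measurements in post-therapy surgical" samples.

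**The concern.** The planned test asks whether values changed between baseline and surgery. The objectives ask whether they changed more than on placebo gel. The two questions coincide only if nothing but the drug moves the measurements, and the sampling scheme gives reason to doubt that. Baseline blood is a screening draw for which section 7.2.1 mentions no fasting. The later draw follows an overnight fast, on the day of surgery, possibly in the operating room. Baseline tissue is a core biopsy, while later tissue comes from the mastectomy specimen.

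Placebo women in Cohorts 1 and 2 go through the same sequence, so they are the control for these shifts. A one-sample test does not use them.

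Section 2.3.1 expects coagulation and estrogenicity changes to be minimal, and tissue markers to be consistent with a therapeutic effect. A shared shift in a coagulation protein or in Ki67 could be taken for a drug effect, and an opposing shift could conceal a real one.

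**Working it through.** **Inputs from the documents.** Cohorts 1 and 2 each have 8 active and 4 placebo women (section 3.2.1). Cohort 3 has 8 active women, not randomised. Tests are two-sided and intervals are 95% (sections 13.5 and 13.8).

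**The plan's own figure.** Pooled placebo is 4 + 4 = 8. Its standard error is SD/√8 = 0.354 SD, and 0.5/√8 = 0.177 for a proportion. Both reproduce section 13.1. The plan gives no power calculation for objectives 1.2.3 to 1.2.6.

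**Assumptions.** The documents give no SD, shift or effect size for these endpoints. I assume normal change scores with a common SD of 1, two-sided alpha 0.05, and a shift *s* shared by active and placebo women over a range from 0 to 1 SD.

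**Why the contrast is protected.** With drug effect *d*, mean change is *d + s* on active gel and *s* on placebo gel. The one-sample test addresses *d + s*. The between-group difference is (*d + s*) − *s* = *d*, so any shared shift cancels.

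**False attribution (*d* = 0).** Rejection rates for the signed-rank test against zero, from 400,000 simulated data sets per setting with exact null tables:

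| Shared shift (SD) | n = 8 | n = 6 |
|---|---|---|
| 0 | 3.9% | 3.1% |
| 0.25 | 7.5% | 5.0% |
| 0.5 | 19.2% | 11.1% |
| 0.75 | 38.5% | 21.3% |
| 1.0 | 61.1% | 35.3% |

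The n = 6 column allows for missing pairs. The exact size of the rank-sum contrast is 4.99% for 8 against 8 and 4.11% for 6 against 6, at any shared shift. The t-test shows the same pattern: with n = 8, the one-sample test rejects 23% at 0.5 SD and 68% at 1.0 SD, while the two-sample test stays near 5%.

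**Masking.** Take a drug effect of 1.0 SD and an opposite shared shift of 1.0 SD, with 8 per group. The signed-rank test detects it 3.9% of the time, which is its null rate. The rank-sum contrast detects it 44% of the time (two-sample t-test: 46%).

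**Price in precision (t-based 95% CI half-width, in SDs of change).**

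- Within one arm of 8: t₇/√8 = 2.365/2.828 = 0.84
- 8 against 8: t₁₄ × √(2/8) = 2.145 × 0.5 = 1.07
- 6 against 6: t₁₀ × √(2/6) = 2.228 × 0.577 = 1.29

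**The case against.** The strongest defence is that placebo was deliberately kept descriptive. Section 13.1 says formal comparison is limited by the sample size and gives the placebo arm the purpose of showing variability without treatment. Section 13.4 expects to learn from placebo without formal testing. Sections 13.2 and 13.8 imply results with CIs for every group, so a careful reader would see a shared shift in the placebo group too. If a reader claims a drug effect only when the active arm is significant and an independent placebo arm of 8 is not, the error rate is 0.192 × 0.808 = 16% at 0.5 SD and 0.611 × 0.389 = 24% at 1.0 SD. The 19% and 61% figures assume that placebo is ignored.

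That reduces the size but does not remove the problem: 16% to 24% is still well above 5%, and significance in one arm but not another is not an estimate of the difference. The section 13.4 remark sits under the primary endpoint. Declining a formal test does not explain the missing estimate, and section 13.5 does plan formal tests, against a different null.

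Three further points stand. No shift is documented, and with none the one-sample test holds its level. The masking example is exact cancellation, the worst case. The endpoints are secondary and partly exploratory, and no dose or stopping rule in the documents depends on them.

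**Conclusion.** The concern holds. Four objectives promise a placebo comparison, and their analyses specify none, although the same section names one for BESS. The false-attribution and masking rates are illustrations, resting on normal change scores and an assumed shared shift of up to 1 SD. The mismatch itself does not depend on those assumptions.

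The consequence is confined to how the secondary results are interpreted. It should be fixed because the needed data are already being collected. The corrected analysis will be an estimate with a wide interval, not a powered test: by the two-sample t-test, 80% power at 8 against 8 needs a difference of about 1.51 SD.

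**What to change.** In section 13.5, replace the analysis for items 3 to 6 with wording such as:

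*The main analysis is the difference in post-minus-pre change between each randomised ENX dose (active arms of Cohorts 1 and 2) and the pooled placebo group, with a Hodges-Lehmann estimate, its 95% CI and the Wilcoxon-Mann-Whitney test named in item 8. These analyses are exploratory. Within-arm changes are descriptive only. Cohort 3, which is not randomised and has no placebo, is shown separately. The number of women with paired samples is stated for each endpoint and group.*

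A baseline-adjusted difference would also serve, but one estimator should be named. Add that a non-significant contrast does not establish the minimal change hypothesised in section 2.3.1, and that readers should look at the CI. Date the revision and label it as made after the interim analysis discussed on April 13, 2020 (section 3.2.1), since both placebo-controlled cohorts were complete by then.

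The cost is wording only. The drawbacks should be stated:

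- The half-width is about 1.07 SD at 8 against 8 and 1.29 SD at 6 against 6.
- Rank-sum power is 44% for a 1.0 SD difference at 8 against 8.
- Placebo is pooled across sequential cohorts.
- Paired tissue may fall below 8 per group, because women having prophylactic mastectomy are eligible and may lack a tumour core biopsy. Section 8.3 also makes non-compliant women not evaluable for secondary endpoints.
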